14.2.7 Sildenafil levels

Peak sildenafil levels (45-120 minutes post dosing) will be determined at the 12 and 24 week visits and will be timed to coincide or immediately precede CPXT.

15. METHODS TO PROMOTE ADHERENCE TO THE INTERVENTIONS

Adherence to study drug: Patients will be instructed to bring all used and remaining bottles of study drug to each study visit. The percent compliance will be calculated at each study visit. Adherence to study procedures: Adherence to study procedures will be enhanced by the following factors:

- 1. At recruitment and consent visits, the entire study will be carefully explained to the patient and figures used to indicate what procedures and visits will be required of the patient. The potential participant will be asked to carefully consider their ability to participate in the study and specifically their willingness to perform a total of four cardiopulmonary exercise tests.
- 2. When feasible, use of a clinically indicated screening CPXT will familiarize the patient with the procedure and better enable the patient to determine whether they are able to perform subsequent baseline, 12 and 24 week CPXT. Further, patients with non-cardiac dyspnea due to frailty, motivational factors, deconditioning and pulmonary disease will be identified and excluded (patients must meet RER≥1.0) since these patients are less likely to perform subsequent CPXT.
- 3. Designation of VO₂ as the primary endpoint emphasizes its importance to both the investigator and the patient and will enhance compliance.
- 4. Adherence to study drug and procedures will be promoted via the study visits and monthly phone visits when not seen in person.
- 5. There is currently no therapy proven to affect outcomes in DHF. This factor generally enhances compliance with an RCT of novel therapies.
- 6. Performance of RELAX within the limited number of sites in the HFN under the direct supervision of the principal investigators involved in the HFN steering committee should enhance compliance with the baseline and follow up studies.
- 7. Data completeness at each site will be carefully monitored by the DCC and those sites not providing complete follow up data will be contacted and strategies to enhance compliance identified.
- 8. In general, event rates in RCT are lower than those observed in observational studies of HF and this was observed in DHF even in a large RCT restricted to elderly persons (PEP-CHF)⁴⁷. Power calculations indicate adequate power even considering death rates at 6 months similar to those observed in community based observational studies.

16. QUALITY CONTROL ACTIVITIES

16.1 Training Sessions and Certification Procedures

A Manual of Operating Procedures (MOP) details all study procedures. It contains specific instructions describing how the study is conducted, what procedures are performed, in what order, by whom and under what circumstances. A study coordinator training session will be held to provide appropriate instruction regarding the RELAX study.

17. PARTICIPANT SAFETY AND ADVERSE EVENTS

17.1 Institutional Review Boards

Before initiating this study, the protocol, site-specific informed consent forms, HIPAA forms, recruitment materials, and other relevant information will be reviewed by a properly constituted IRB at each participating clinical site. A copy of the signed and dated IRB approval at each clinical site will be retrieved prior to site activation and archived at the DCC. Any amendments to the protocol, other than simple administrative and typographical changes, must be approved by each IRB before they are implemented. The sites will seek annual renewals of their IRB approvals in accordance with local procedures.

17.2 Adverse Events

During a clinical trial, the reporting of adverse experience information can lead to important changes in the way a new treatment is developed, as well as provide integral safety data.

17.2.1 Definition of an Adverse Event

An adverse event (AE) is any untoward medical occurrence in a patient or clinical-investigation subject administered a pharmaceutical product and which does not necessarily have to have a causal relationship with this study drug. An AE can, therefore, be any unfavorable and unintended sign (including an abnormal laboratory finding, for example), symptom, or disease temporarily associated with the use of a medicinal product, whether or not considered to be related to the medicinal product. Diseases, signs, symptoms, or laboratory abnormalities already existing at enrollment are not considered AEs unless they worsen (i.e., increase in intensity or frequency). Surgical procedures themselves are not AEs; they are therapeutic measures for conditions that require surgery. The condition for which the surgery is required may be an AE. Surgical procedures planned prior to randomization and the conditions leading to these measures are not AEs.

The relation between an adverse event and the study drug will be determined by the Investigator on the basis of his or her clinical judgment and the following definitions:

Reasonable Possibility – There is a reasonable possibility that the adverse event was caused by the study drug. The temporal relationship of the adverse event to study drug administration makes a causal relationship possible, and other drugs, therapeutic interventions or underlying conditions do not provide sufficient explanation for the observed event.

Not a reasonable possibility – There is not a reasonable possibility that the adverse event may have been caused by the study drug. The temporal relationship of the adverse event to trial drug administration makes a causal relationship unlikely, or other drugs, therapeutic interventions or underlying conditions provide sufficient explanation for the observed event.

Drug-related means that there is a reasonable possibility that the adverse event may have been caused by the test agent.

An **unexpected** adverse event is an adverse reaction, the nature or severity of which is not consistent with the applicable product information (e.g., U.S. package insert).

The intensity of the adverse event will be defined by the following criteria:

- Mild: The adverse event is noticeable to the patient but does not interfere with routine activity
- Moderate: The adverse event is discomforting and interferes with routine activity.
- Severe: The adverse event significantly limits the patient's ability to perform routine activities despite symptomatic therapy.

Life -Threatening: The patient is at immediate risk of death.

17.2.2 Adverse events Anticipated in This Study

The following table separates the definite or probable study drug-related conditions, illnesses or adverse events from the pre-existing or concurrent illnesses seen in the study patient population.

Pre-existing, Predisposed or Concurrent Conditions, Illnesses or Adverse Events	Study Drug Related Conditions, Illnesses or Adverse Events				
 Sudden death Arrhythmias Acute coronary syndrome Cerebrovascular accident Pulmonary embolism Hospitalizations for HF IV diuretic administration Deep vein thrombosis Dizziness Lightheadedness Syncope Worsening renal function 	 Headache Flushing Dizziness, Lightheadedness Syncope Dyspepsia Worsening renal function Visual disturbance Priapism Tinnitus or hearing loss 				

17.3 Adverse Event Collection

For the RELAX trial, all AEs (serious and non-serious) will be recorded from start of study treatment through final study visit on the AE case report form.

17.4 Serious Adverse Events

A serious adverse event (SAE) is any untoward event that:

- Is fatal
- Is life-threatening
- Requires inpatient hospitalization or prolongation of existing hospitalization, with the following exceptions:
 - Preplanned (prior to the study) hospital admissions unless the hospitalization is prolonged
 - Planned admissions (as part of a study, e.g., routine biopsies)

- Hospitalizations of less than 24 hours duration
- Hospitalization for elective procedure
- Emergency room visits
- Results in persistent or significant disability or incapacity.
- Is a congenital anomaly or birth defect.
- Important medical events that may not result in death, be life-threatening, or require inpatient hospitalization may be considered an SAE when, based on appropriate medical judgment, they may jeopardize the patient and may require medical or surgical intervention to prevent one of the outcomes listed above.

Life-threatening means that the patient or subject was, in the view of the investigator, at immediate risk of death from the AE as it occurred. It does not include an AE that, had it occurred in a more severe form, might have caused death.

Persistent or significant disability/incapacity means that the event resulted in permanent or significant and substantial disruption of the subject's ability to carry out normal life functions.

Associated with the use of the drug means that there is a reasonable possibility that the experience may have been caused by the drug.

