9.5 Side Effects

The known side effects of sildenafil include the following: *Prevalence > 10%:* Central nervous system: headache *Prevalence 1% to 10%:* Cardiovascular: flushing Central nervous system: dizziness Dermatologic: rash Genitourinary: urinary tract infection Ophthalmic: abnormal vision (color changes, blurred or increased sensitivity to light) Respiratory: nasal congestion *Prevalence < 2% (limited to important or life-threatening):*

Allergic reaction, angina pectoris, anorgasmia, asthma, AV block, cardiac arrest, cardiomyopathy, cataract, cerebral thrombosis, colitis, dyspnea, edema, exfoliative dermatitis, eye hemorrhage, gout, heart failure, hyperglycemia, hypotension, migraine, myocardial ischemia, neuralgia, photosensitivity, postural hypotension, priapism, rectal hemorrhage, seizure, shock, syncope, vertigo, tinnitus, transient or permanent unilateral or bilateral hearing loss.

In regards to potential toxicity, side effect prevalence was not dose dependent in the SUPER trial. Most adverse events were mild to moderate for all treatment groups and were not dose related as outlined above. Over 12 weeks, only two serious adverse events, postural hypotension and left ventricular dysfunction, were considered to be related to sildenafil. In contrast, in a large meta-analyses of 27 erectile dysfunction trials in 6659 men, studies which examined dose responsiveness did demonstrate a trend towards a dose response in the prevalence of side effects⁸⁵. However, the rate of discontinuation for side effects was lower in the active vs placebo arms. Side effects were not serious and the incidence of chest pain, myocardial infarction or death was not increased in premarketing or postmarketing studies. In this metaanalysis, there was no apparent increase in side effects according to baseline characteristics (age, diabetes, etc).

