17.5 Procedures for Expedited Reporting of SAE

For the RELAX trial, all SAEs occurring from study drug initiation through final study visit require expedited reporting. The investigator must complete and submit a Pfizer IIR SAE form to DCRI Safety Surveillance within 24 hours of knowledge of the event.

DCRI Safety Surveillance [contact] [contact]

The investigator must complete and submit a follow-up Pfizer IIR SAE form when important follow-up information (diagnosis, outcome, results of specific investigations, etc.) becomes available after submission of the initial form. Follow-up forms should be submitted according to the same process used for reporting the initial event as described above (i.e., within 24 hours of knowledge). All reportable events will be followed until resolution, stabilization, or 30 days after the last patient completes the final study visit, whichever occurs first. The investigators will be responsible for reporting AEs to their local institutional review boards (IRBs) in accordance with local guidelines.

DCRI Safety Surveillance will perform a clinical review of the forms to verify that all sections are complete, legible and consistent and will query the site for incomplete information, data clarification and/or follow-up information. A narrative summary will be written for each SAE and SAE data will be entered into the Clintrial database.

DCRI Safety Surveillance will forward all SAE forms, regardless of relatedness, to Pfizer within 1 business day of receipt along with a copy of any gueries sent to the site.

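### The unqualified elective-procedure exception in Section 17.4 lets a condition that begins or worsens on study drug miss SAE status when an elective admission of 24 hours or more is its only ground for seriousness

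*Protocol*

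**What the plan says.** Section 17.4 lists the criteria that make an event serious. The admission criterion reads "Requires inpatient hospitalization or prolongation of existing hospitalization, with the following exceptions". Among the exceptions are "Preplanned (prior to the study) hospital admissions unless the hospitalization is prolonged", admissions planned as part of a study, stays shorter than 24 hours, emergency room visits and, with no further words, "Hospitalization for elective procedure".

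The same section keeps a judgment-based route: "Important medical events that may not result in death, be life-threatening, or require inpatient hospitalization may be considered an SAE when" the investigator's medical judgment is that the patient may be at risk and may need intervention to prevent one of the listed outcomes.

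Section 17.2.1 sets the AE-level rule for surgery: "Surgical procedures planned prior to randomization and the conditions leading to these measures are not AEs". It adds that the condition behind an operation may itself be an AE, and that a condition present at enrollment becomes one if it worsens.

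Section 17.3 states that "all AEs (serious and non-serious) will be recorded from start of study treatment through final study visit on the AE case report form". Section 17.5 states that "all SAEs occurring from study drug initiation through final study visit require expedited reporting".

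**The concern.** The AE section asks when the condition arose, whether it has worsened, and when the surgery was planned. The elective exception in the SAE section asks only how the admission was scheduled. Scheduling does not show whether a condition arose on study drug, or how serious it is.

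The exception can reach events that matter for this drug. Section 9.5 gives, among known but uncommon effects of sildenafil, "Allergic reaction, angina pectoris, anorgasmia, asthma, AV block, cardiac arrest, cardiomyopathy, cataract, cerebral thrombosis". The same section makes AV block a reason to stop study drug. Yet new AV block leading to a scheduled pacemaker admission, or new angina leading to scheduled revascularization, would not be serious on the admission criterion.

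What depends on the SAE label is set out in Section 17.5: the report within 24 hours, the central clinical review, the written narrative and the forwarding to the manufacturer. The SAE comparison between arms depends on it too.

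**Working it through.** No arithmetic applies. The check is to read the rules together and follow a treatment-emergent condition through them.

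**What the elective exception adds.** In the extracted text a page break sets this bullet level with the main criteria. It must still be an exception, because the neighbouring bullet on stays under 24 hours makes no sense as a ground for seriousness. Two other bullets already cover admissions planned before the study and admissions planned as part of a study. What the elective bullet adds is therefore elective admissions arranged after entry, and nothing in it separates old conditions from new or worsened ones.

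**Four cases for a condition that begins or worsens on study drug:**

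1. Unplanned inpatient admission of 24 hours or more: serious by the admission criterion, and reported within 24 hours.
2. Elective admission, with another criterion met (fatal, life-threatening, disabling, birth defect): serious through that criterion, and reported within 24 hours.
3. Elective admission of 24 hours or more, with no other criterion met: not serious by the admission criterion. It is recorded on the AE form and becomes an SAE only if the investigator applies the important-medical-event clause.
4. Admission of less than 24 hours, with no other criterion met: excepted by the duration bullet whatever the elective bullet says.

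The gap is case 3 alone.

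**Comparison with Section 17.2.1.** There, surgery and its underlying condition are set aside only if the surgery was planned before randomization, and a pre-existing condition that worsens is an AE. A case 3 event is therefore an AE under 17.2.1 but falls under an exception in 17.4 that has no timing limit.

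**Size.** The protocol gives no rate of elective admissions, no lengths of stay, and no estimate of how often investigators would apply the judgment clause. The number of case 3 events cannot be derived from it.

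**The case against.** The strongest reply is that little is lost. The exception switches off one criterion only. The important-medical-event clause plainly fits the examples: new AV block needing a pacemaker is a condition that may require intervention to prevent a worse outcome. All AEs are recorded and, under Section 18.2, presented by treatment group, and Section 20.3 provides a safety monitoring board. Nor is there a strict contradiction, since 17.2.1 defines what is an AE and 17.4 defines what is serious, and an event can be the first without the second.

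Most of this stands, and it limits the point to case 3. It does not close case 3. The clause is permissive, may be applied differently across sites, and sits beside a bullet that gives an investigator a textual reason not to report. Recording on the AE form does not trigger the 24-hour report or the central review.

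A reader might infer more than the documents support:

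- **That treatment-emergent events needing admission generally escape SAE status.** They do not. Cases 1 and 2 remain SAEs. Section 17.4.1 also names acute coronary syndrome and visual disturbance as anticipated SAEs without tying them to an admission.
- **That the MedWatch form in Section 17.5.1 is lost for the known effects.** That form also requires the event to be unexpected under the package labeling. Known effects that the labeling lists would generally not qualify in any case.
- **That the composite score and the safety data would disagree.** Section 14.2.1 ranks cardiovascular and renal admissions by primary cause and does not say how elective ones are handled. A ranking rule and a seriousness definition also need not coincide.
- **That the sildenafil arm is undercounted.** This would follow only if the drug caused such events and they were managed by elective admission. The protocol does not show that.

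**Conclusion.** The point holds for a narrow residual class: a condition that begins or worsens on study drug, leads to an elective admission of 24 hours or more, and meets no other seriousness criterion. As the protocol is written, such an event is an SAE only at the investigator's discretion, so it can miss the 24-hour report, the central review and the SAE count. It is not lost from the AE data.

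This rests on reading the elective bullet as an exception to the admission criterion and as additional to the preplanned bullet. Its size is unknown, and any count would rest on an assumed rate. It is a worthwhile, inexpensive tightening of a stated rule, with no bearing on the efficacy analysis.

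**What to change.** In Section 17.4, replace the elective bullet with: *hospitalization for an elective procedure for a condition present before the first dose of study drug that has not worsened since*. Carry the same wording into the SAE form instructions.

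This brings the exception into line with the timing-and-worsening logic of Section 17.2.1. Anchoring it to the first dose matches the start of AE recording in 17.3 and of expedited reporting in 17.5. Section 13.1 puts randomization and initial dosing at the same week 0 visit, so the different anchor in 17.2.1 should make little practical difference.

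The cost is one clause and a few more SAE forms. Elective stays under 24 hours remain excepted by their own bullet, and this change does not touch them. No treatment or stopping rule is affected.

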17.4.1 Potential SAEs Anticipated in This Study

Serious adverse events anticipated based on the proposed study population and on use of the study drug in previous large randomized clinical trials for erectile dysfunction or pulmonary hypertension include:

- 1. Death
- 2. Worsening HF as defined by the need for escalation of HF therapy as an outpatient
- 3. Unplanned treatment for HF in an Emergency Department without hospital admission
- 4. Unplanned hospitalization for HF
- 5. Syncope
- 6. Visual disturbance
- 7. Priapism
- 8. Cerebrovascular accident
- 9. Acute coronary syndrome
- 10. Hearing loss

17.5 Procedures for Expedited Reporting of SAE

For the RELAX trial, all SAEs occurring from study drug initiation through final study visit require expedited reporting. The investigator must complete and submit a Pfizer IIR SAE form to DCRI Safety Surveillance within 24 hours of knowledge of the event.

DCRI Safety Surveillance [contact] [contact]

The investigator must complete and submit a follow-up Pfizer IIR SAE form when important follow-up information (diagnosis, outcome, results of specific investigations, etc.) becomes available after submission of the initial form. Follow-up forms should be submitted according to the same process used for reporting the initial event as described above (i.e., within 24 hours of knowledge). All reportable events will be followed until resolution, stabilization, or 30 days after the last patient completes the final study visit, whichever occurs first. The investigators will be responsible for reporting AEs to their local institutional review boards (IRBs) in accordance with local guidelines.

DCRI Safety Surveillance will perform a clinical review of the forms to verify that all sections are complete, legible and consistent and will query the site for incomplete information, data clarification and/or follow-up information. A narrative summary will be written for each SAE and SAE data will be entered into the Clintrial database.

DCRI Safety Surveillance will forward all SAE forms, regardless of relatedness, to Pfizer within 1 business day of receipt along with a copy of any gueries sent to the site.

17.5.1 Regulatory Reporting

For any SAE that is assessed by the site investigator as both related to study drug (reasonable possibilty) and as unexpected per package labeling, site investigators are required to complete and submit the voluntary 3500 MedWatch form online at https://www.accessdata.fda.gov/scripts/medwatch/. A copy of this MedWatch form should be sent to DCRI Safety Surveillance. Investigators are responsible for promptly reporting these events to their reviewing IRBs.

18. STATISTICAL CONSIDERATIONS

18.1 Sample Size and Power Considerations

18.1.1 Primary endpoint: Change in peak VO₂ (\triangle VO₂)

No previous study has characterized the standard deviation of the ΔVO_2 in a study population similar to that planned here where DHF patients are studied and strict entry criteria and a screening cardiopulmonary exercise test (CPXT) are used to minimize enrollment of patients with non-cardiac dyspnea and select for patients who can perform near maximal exercise (RER≥1.0). Patients who are unwilling or unable to perform at this level of exercise will not be eligible for enrollment. This requirement will reduce variability in both the primary endpoint (Δ peak VO₂) and the secondary endpoint measuring submaximal exercise (\alpha 6MW). Recognizing the lack of data relevant to the planned study population, we have based power calculations on the SD for the ΔVO_2 observed in randomized clinical trials (RCT) in SHF where ΔVO₂ was a primary (SD=2.7 ml/kg/min)¹¹¹ or secondary (SD≈2.7 ml/kg/min) ^{112,113} endpoint and on limited RCT data in DHF⁵⁰ (SD=1.3 ml/kg/min; [name], personal communication). A range of withdrawal due to death at 6 months was also estimated based on a large RCT in DHF (<2%)⁴⁷ and community based observational studies in DHF (13-16%)^{7,11}.

Power	85% Power			90% Power			analysis indicates that a sar	
	TE = 1.0 ml/kg/min	nin ml/kg/min	ml/kg/min ml/	TE = 1.0 ml/kg/min 172	TE = 1.2 ml/kg/min 120	TE =1.5 ml/kg/min	1.2 ml/kg/min in ΔVO_2 with	
SD=2.0	146					78		
SD=2.5	228	158	102	266	186	120	SD of ΔVO_2 =2.5 ml/kg/min. account for up to 25% mis	
SD=3.0	326	228 146	382	266	172	data, the projected sample s		
							is approximately 215 patients In patients with SHF, a si dose of sildenafil resulted in	

The relationship between power, effect size (mean difference in ΔVO_2) and SD of the ΔVO_2 using a two sample t-test and a two-sided alpha of 0.05 is shown in the table assuming 85% and 90% power. This

dose of sildenafil resulted in statistically significant increases in

TE=treatment effect (difference in Δ in peak VO2); SD = standard deviation of Δ in peak VO2

peak VO₂ in three small, single center studies (n≤24 patients) and the magnitude of this effect was similar to or exceeded that detectable in the current study^{64,70,114}. Data from two recent studies of chronic PDE-5 inhibition in SHF showed significantly greater increases in peak VO2 in sildenafil vs placebo treated patients with effect sizes of 1.7 and 2.0 ml/kg/mn^{115,116}. As outlined in the Preliminary Studies (Section 5.0), we hypothesize that we will observe a greater effect in DHF than SHF and with chronic vs acute therapy.

The RELAX trial is designed to test the hypothesis that chronic PDE-5 inhibition improves exercise capacity and clinical status in DHF *and* to explore the mechanisms responsible for such an effect. If treatment benefits for exercise performance and key pathophysiological mechanisms are demonstrated, a larger clinical outcome based trial may be warranted.

